7.3 Center Pooling

Due to the feasibility nature of this study and reduced sample size, statistical comparisons of sites' performance will not be performed.

7.4 Handling of Missing, Unused, and Spurious Data and Dropouts

Missing data will not be imputed. An adjudicated COPD event will be considered in the analysis to assess changes in LINQ™ derived data if it has device data before and after the event onset date.

7.5 Adjustments for Multiple Comparisons

No adjustment for multiple comparisons will be made since this is a single-arm study.

7.6 Demographic and Other Baseline Characteristics

Baseline data such as demographics, medical history, physical exam (heart rate, blood pressure, weight, spirometry assessment, etc.), and blood measurements (Creatinine, BNP, NT-pro BNP, White Blood Cells and Eosinophils) will be summarized using descriptive statistics.

For categorical data such as gender, counts and percentages will be employed, while for continuous variables such as age, means, standard deviation, quartiles, minimum, and maximum will be provided. These statistics will be provided both for all enrolled subjects and for the subset of subjects who will be analyzed for the primary objective described in section 7.1.3.

7.7 Treatment Characteristics

Descriptive statistics will be used to summarize all procedure information collected, including

- Procedure location
- Location of inserted device (e.g. parallel to sternum over 4th intercostal space)
- Number of repositioning/modifications during the insertion procedure
- Whether device was sutured
- Closure method used (e.g. staple(s), suture(s))
- Whether topical skin adhesive/Dermabond (Registered) was applied per its labelling if used
- Whether LINQ HF Investigational RAMware was successfully downloaded

Additionally, the percentage of subjects on CV and pulmonary medications will be assessed as of each follow-up visit.

7.8 Interim Analyses

No interim analyses are planned for this study. Therefore, there are no criteria for early termination based on statistical evidence.

7.9 Evaluation of Objectives

The primary objective is to characterize Reveal LINQ™ derived data from patients with COPD by assessing the relationship between changes in LINQ™ derived data with subsequent COPD events.

7.9.1 Hypothesis

There is no statistical hypothesis for this objective.

7.9.2 Endpoint Definition

The COPD events as adjudicated by the Event Adjudication Committee (EAC) will be used in the analysis. In the case where a subject has multiple COPD events per EAC adjudication during the study, all the COPD events of the subject will be included in the analysis.

A COPD event is defined as an adverse event where the underlying COPD condition exacerbates beyond normal day-to-day variations, where an increase in dyspnea, cough, and/or sputum production presents with acute onset and necessitates supplementing regular COPD medications with antibiotics for respiratory pathogens and/or steroids.

7.9.3 Analysis Methods

Data from multiple study components will be collected in this study, of which the Reveal LINQ™ HF derived data is of the most interest. This includes subcutaneous electrocardiogram, impedance, temperature, accelerometer and patient activity measurements.

Descriptive statistics such as mean and standard deviation for continuous variables and count and proportion for categorical variables will be used to summarize the derived data from Reveal LINQ™ HF. The relationship between changes in LINQ™ derived data and COPD events per EAC adjudication will be evaluated. Specifically, for each subject that has experienced at least one COPD event per EAC adjudication, the average daily measurements of LINQ™ derived data before and after a COPD event will be plotted to identify patterns and signals related to the occurrence of the COPD event.

In addition, exploratory survival analyses for time to first COPD event through 12-months of follow-up such as a Kaplan-Meier curve and Cox proportional hazards regression models with independent variables such as demographics and comorbidities will be included.

Each subject's time to first detected and adjudicated COPD event will be defined as the time from insertion date to the onset date of first COPD event. Subjects who have not experienced a COPD event through 12 months will be censored at:

- (1) their point of last contact, usable Reveal LINQ ICM interrogation or CareLink transmission if they occur before or at 12 months, whichever is later

or

- (2) 12 months (374 days) if their point of last contact, usable Reveal LINQ ICM interrogation or CareLink transmission go beyond 12 months.

Survival estimates and hazard rate with 95% confidence intervals will be reported.

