## 4.2 Purpose

The ability to predict which patients will subsequently have an exacerbation for COPD using the traditional evaluation measures such as physical signs and symptoms is limited. Medical interventional methods currently may not identify patients early enough to prevent an exacerbation. To help reduce these exacerbations and improve disease management, sensors in a minimally invasive device can be used to identify factors that are associated with exacerbations. Thus, a solution to continuously monitor COPD patients at risk for acute exacerbations (GOLD stage C/D) in an ambulatory fashion to predict symptom worsening and provide timely remote intervention to prevent hospitalizations is an unmet clinical and economic need. Using sensors in a minimally invasive device like LINQ™ to sense, predict and prevent COPD hospitalizations is the overarching objective of this project. As a first step, the LINQ-COPD study aims to collect sensor data to characterize the changes in these sensor data prior to COPD hospitalizations with the aim to develop a prediction algorithm that can identify when patients are at risk and may benefit from a remote intervention.

Prior studies have shown implantable device-measured diagnostics like intra-thoracic impedance, AF burden, heart rate metrics, respiration, and patient activity metrics can be used individually or in a

combined fashion to identify when patients are at risk for certain events. We hypothesize that these measurements made in the subcutaneous thoracic space may be sensitive enough to detect physiological changes associated with COPD.

The use of implantable device features such as the OptiVol™ impedance algorithm is clinically useful in monitoring thoracic fluid status for pacemaker or ICDs and may be measured in the subcutaneous space. The Monitoring in Dialysis (MiD) study was conducted in renal failure patients implanted with a Reveal LINQ™ insertable cardiac monitor. The results indicated impedance trends upwards with fluid removal during dialysis sessions and downwards between dialysis sessions. Therefore, the preliminary data show that continuous impedance monitoring has a direct inverse relationship to patient thoracic fluid status in both a detailed analysis and long-term trending analysis.

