## 10.10 Weekly Subject Diary

Subjects will complete diary submissions at least once a week or when their COPD symptoms change, which can be more often than once per week. The diary comprises of the Breathlessness, Coughing and Sputum Scale Questionnaire (BCSS) and PRN medication tracking. The subject will receive instructions on how to complete the weekly diary, refer to Section 18.3 for more details.

The diary data will be reviewed alongside the CRF and LINQ™ device data to track potential COPD events. The subject diary data will not be reviewed for any reportable AEs since all pertinent AEs will be formally collected at the scheduled follow up visits.

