## 10.18 Medications Assessment

The name, dose, frequency and route of all medications will be collected at all visits. Changes to medications will be captured on the Medication Log eCRF.

There are no medications that are required for this study although some medications may be administered in treating specific conditions at the discretion of the physician. The only medications that are excluded from use during this study are investigational.

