### 14.3.3 Analysis Methods

Data from multiple study components will be collected in this study, of which the Reveal LINQ™ HF derived data is of the most interest. This includes subcutaneous electrocardiogram, impedance, temperature, accelerometer and patient activity measurements.

Descriptive statistics such as mean and standard deviation for continuous variables and count and proportion for categorical variables will be used to summarize the derived data from Reveal LINQ™ HF. The relationship between changes in LINQ™ derived data and COPD events per EAC adjudication will be evaluated. Specifically, for each subject that has experienced at least one COPD event per EAC adjudication, the average daily measurements of LINQ™ derived data before and after a COPD event will be plotted to identify patterns and signals related to the occurrence of the COPD event.

Baseline data such as demographics, medical history, physical exam (heart rate, blood pressure, weight, spirometry assessment, etc.), and blood measurements (Creatinine, BNP, NT-pro BNP, White Blood Cells and Eosinophils) will also be summarized using descriptive statistics.

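### The event plots align LINQ data to onset only; recorded PRN use and medication changes should be overlaid, because event and treatment cannot otherwise be told apart

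*SAP*

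**What the plan says.** The primary analysis is graphical. SAP 7.9.3 states that "the average daily measurements of LINQ™ derived data before and after a COPD event will be plotted to identify patterns and signals", and Protocol 14.3.3 has the same plan ("the average daily measurements of LINQ™ derived data before and after a COPD event will be plotted"). Under SAP 7.4 an adjudicated event is used "if it has device data before and after the event onset date", so onset divides the record. No treatment variable is named.

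The event definition in SAP 7.9.2 contains treatment: the exacerbation "necessitates supplementing regular COPD medications with antibiotics for respiratory pathogens and/or steroids".

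Treatment information is collected in two places. Protocol 10.10: "The diary comprises of the Breathlessness, Coughing and Sputum Scale Questionnaire (BCSS) and PRN medication tracking". Protocol 10.18: "Changes to medications will be captured on the Medication Log eCRF". The SAP's one dedicated medication summary is in 7.7, where "the percentage of subjects on CV and pulmonary medications will be assessed as of each follow-up visit"; that table is not aligned to events. SAP 7.10 also plans a listing of all adverse events that includes a summary of actions taken, again not joined to sensor data.

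**The concern.** Protocol 4.2 sets the aim: sensor changes that come before an event, feeding an algorithm that identifies patients who may benefit from remote intervention. SAP 7.9 likewise concerns subsequent events. For that aim, a sensor shift that precedes any change in medication is worth more than one that follows a reliever or drug change already made. The planned plots show both alike.

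At least one of the plotted signals could plausibly respond to treatment. Protocol 4.2 reports that "continuous impedance monitoring has a direct inverse relationship to patient thoracic fluid status", so a drug change that alters fluid status could move impedance. After onset the problem is structural: every analysed event is treated, so there is no untreated event to compare with, and only the timing of treatment can help. The plots are the main output and are meant to support algorithm development (Protocol 4.2 and 6.2), so a wrong attribution would carry forward.

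**Working it through.** **1. The plan's own event count.** Inputs from SAP 6 and Protocol 14.4: 60 subjects, 12 months, 2 exacerbations per patient-year, 50% meeting the COPD event definition.

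- 60 × 1 × 2 = 120 exacerbations
- 120 × 0.50 = 60 COPD events

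Both stated figures reproduce, and nothing in this point changes them.

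**2. Share of events that are treated.** By the definition in SAP 7.9.2, 60 of 60 (100%) involve added antibiotics and/or steroids. Treatment given for the event would normally follow onset, so this bears mainly on the post-onset half of each plot.

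**3. What is recorded, and how finely.**

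| Source | Content | Timing | Used in event plots? |
|---|---|---|---|
| LINQ data (SAP 7.9.3) | Sensor averages | Daily | Yes |
| Adverse event onset (SAP 7.4) | Date | Day | Yes |
| Diary (Protocol 10.10) | BCSS, PRN use | At least weekly, or when symptoms change; SAP 3, 5 and 7.1.1 say daily | No |
| Medication Log (Protocol 10.18) | Medication changes | Date fields not shown; eCRFs are under separate cover (Protocol 18.2) | No |
| Visit table (SAP 7.7) | Percentage on CV and pulmonary drugs | Each follow-up visit; targets 90 days apart (Protocol 10.3, Table 6) | No |

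Protocol 14.5 says the SAP will document all pre-specified analyses. An overlay that the SAP does not mention is therefore not planned.

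**4. How much it could matter before onset.** The documents give neither the share of events with a PRN increase or drug change before onset nor the effect of treatment on the sensors. The values below are assumptions, shown as a range. Let *f* be the share of the 60 events so affected, and *d* the treatment-caused shift in SD units of the event-level sensor change.

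- Unaffected events = 60 × (1 − *f*)
- Shift of the averaged curve = *f* × *d*
- Standard error for 60 independent events = 1/√60 = 0.129 SD
- Ratio = *f* × *d* × √60

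| *f* | Unaffected events | *d* | Shift (SD) | Shift / SE |
|---|---|---|---|---|
| 0.25 | 45 | 0.25 | 0.0625 | 0.48 |
| 0.25 | 45 | 0.50 | 0.125 | 0.97 |
| 0.50 | 30 | 0.25 | 0.125 | 0.97 |
| 0.50 | 30 | 0.50 | 0.25 | 1.94 |
| 0.75 | 15 | 0.25 | 0.1875 | 1.45 |
| 0.75 | 15 | 0.50 | 0.375 | 2.90 |

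The range goes from unimportant to large enough to look like a pattern. Subjects may contribute several events, so independence is also an assumption; positive correlation within subjects would raise the standard error and lower the ratios.

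**The case against.** The strongest reply has four parts.

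- **The study is exploratory.** It has no hypothesis (SAP 7.9.1) and looks only for potential patterns. This stands. It makes the point an improvement to a display, not a threat to a formal conclusion.
- **Treatment is not wholly ignored.** Protocol 10.10 has diary data reviewed beside the CRF and device data, and the SAP 7.10 listing should plausibly show the treatment given for each event. Both are true. But the diary review is for tracking possible events, and neither source is joined to the plots.
- **The pre-onset mechanism is thin.** The documents do not say that reliever use moves any sensor or that it clusters before onset. The impedance statement in Protocol 4.2 comes from dialysis patients. If onset is dated from the acute rise in symptoms, symptom-driven PRN use may fall at or after onset. This stands, and it is why the bias is left unquantified.
- **PRN use may be part of the developing exacerbation.** A sensor change that accompanies it can still predict the event. Discarding those days removes the ones nearest onset and could erase true signal. This stands and shapes the fix.

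A reader might infer that treatment effects *would* be taken for event signals, or that most pre-onset windows are affected. The documents support neither, since they give no size or timing. A reader might also fault the visit table in SAP 7.7 for missing short treatment courses, but that table does not claim to capture them.

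**Conclusion.** The gap is real and limited. The plots use onset as their only marker, although PRN use and medication changes are collected. Once treatment starts, event and treatment are mixed in every analysed event by definition (60 of 60 on the plan's projection). Before onset, the plots cannot place a sensor change before or after a recorded reliever or drug change. Whether that biases the pre-onset pattern is unknown: 0.5 to 2.9 standard errors under the assumptions above, which are illustrative and not drawn from the documents. No sample-size or error-rate figure depends on this. It is a specific, low-cost improvement that changes what the plots can support.

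**What to change.** Amend SAP 7.9.3 and Protocol 14.3.3 as follows.

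1. Overlay on each event plot the recorded PRN use and the recorded starts, stops and changes of antibiotics, steroids, bronchodilators and cardiovascular drugs, including diuretics.
2. Summarise the pre-onset window separately from data after treatment starts, and state that the latter is not read as the effect of the event alone.
3. Beside the all-events summary, add a supplementary sensitivity summary of the pre-onset pattern for events (or days) with no recorded PRN increase or drug change. Do not make it a condition for claiming a signal.

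Two preconditions apply. Reconcile the diary frequency (at least weekly in Protocol 10.10; daily in SAP 3, 5 and 7.1.1), and confirm in the eCRFs that medication and PRN entries carry usable dates.

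The cost is revised text and a dataset merge, with no new procedures or subjects. The sensitivity summary will rest on fewer events or days. PRN timing will be only as fine as the diary, which with weekly entries could mean up to 7 days of uncertainty against daily sensor averages.

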## 10.11 Bi-Weekly CareLink Transmissions

Subjects will be provided with a MyCareLink Patient Monitor and enrolled in the Medtronic CareLink network, and will be instructed on how to set up their monitor to support automatic nightly transmission of their device data. In addition, subjects are required to perform a manual device transmission bi-weekly (every 14 days) from the time they are enrolled in the study until they are exited from the study. This transmission is critical as data collected by the investigational RAMware will be overwritten if not manually transmitted within 32 days.

As described above, the subjects are required to complete a bi-weekly transmission. A report will be made available to the site identifying subjects who have missed their manual transmission.

A monthly study deviation will be required if 2 straight bi-weekly transmissions are missed, unless a device interrogation file for an interrogation occurring within the required timeframe is provided to Medtronic.

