## 10.20 Review of Data Recorded by the Reveal LINQ™ Device

Reveal LINQ™ data derived from the investigational RAMware will not be viewable to the site. The standard arrhythmia data from the LINQ™ device will be viewable via CareLink.

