## 10.23 Subject Exit, Withdrawal or Discontinuation

### 10.23.1 Study Exit

Study exit is defined as the moment when a subject officially stops participating in the study. Subjects will be considered exited upon completion of the study exit e-CRF. Prior to exiting a subject from the study, it is recommended to follow the subject until any ongoing AEs related to the Reveal LINQ™ system or procedure are classified by the investigator, as resolved. The date and reason for subject exit must be reported to Medtronic at the earliest opportunity via eCRF. Exited subjects will not be replaced. Upon exiting from the study, no further study data will be collected, or study visits will occur for the subject. All data available through the time of the subject's exit will be used for analysis. Subjects are urged to remain in the study as long as possible but may be exited from the study for any of the following situations:

- Subject did not meet inclusion/exclusion criteria and was not inserted with a LINQ™ device
- LINQ™ ICM explanted and not replaced with a new LINQ™ ICM (e.g. diagnosis determined, suspected infection, subject request, physician determination)
- Subject chooses to withdraw (e.g., consent withdrawal, relocation to another geographic location)
- Investigator chooses to withdraw a subject (e.g., medically justified, inclusion/exclusion criteria not met, failure of subject to maintain adequate study compliance)
- Implant attempted, however no Reveal LINQ™ was implanted
- Subject lost to follow-up
- Death
- Study completion or termination

The following information/procedure is to be collected/Performed at study exit:

- Date of exit
- Reason for exit
- Medications Assessment
- St. George's Respiratory Questionnaire

- Laboratory results: Creatinine, Brain natriuretic peptide (BNP) OR N-terminal brain natriuretic peptide (NT-proBNP), White blood cells, Eosinophils
- Initial Device Interrogation (save to media via USB) (prior to removal)
- Removal of the investigational RAMware from the LINQ™ device
- Opting out of the subject diary
- Post Device interrogation (save to media via USB) (post removal)
- Adverse events
- Device deficiencies
- Study deviations

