## 10.23.3 Lost to Follow-up

In the case that the subject is determined to be lost to follow-up, details of a minimum of two attempts and the method of attempt (e.g., one letter and one phone record or two letters) to contact the subject must be recorded. In addition, follow the regulations set forth by the governing IRB/EC.

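### In the exploratory time-to-first-COPD-event analysis, a CareLink transmission alone can set the censoring date, so time after the last adverse-event check may count as event-free (low importance)

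*SAP*

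**What the plan says.** SAP 7.9.3 adds exploratory survival analyses of time to first COPD event through 12 months: a Kaplan-Meier curve and Cox models, with survival estimates and a hazard rate reported with 95% confidence intervals. Subjects without an event are censored under two rules. Rule (1) uses "their point of last contact, usable Reveal LINQ ICM interrogation or CareLink transmission if they occur before or at 12 months, whichever is later". Rule (2) uses "12 months (374 days) if their point of last contact, usable Reveal LINQ ICM interrogation or CareLink transmission go beyond 12 months".

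The event itself comes from a different source. SAP 7.9.2 states: "The COPD events as adjudicated by the Event Adjudication Committee (EAC) will be used in the analysis".

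On transmissions, protocol 10.11 has the home monitor set up to "support automatic nightly transmission of their device data", and also requires a manual transmission from the subject every 14 days. Protocol 10.20 says the "data derived from the investigational RAMware will not be viewable to the site".

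On adverse events, protocol 10.10 says they are formally collected at scheduled follow-up visits and that the diary is not reviewed for reportable ones. Protocol 10.12.1 sets those visits every three months. Protocol 10.6 asks for events to be reported as they occur, and 10.23.1 includes adverse events in the exit data.

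**The concern.** A censoring date asserts that the subject was known to be event-free until then. Here the event exists in the data only if the site learns of it and reports it. A transmission shows that the device and monitor work; it involves no adverse-event enquiry. Yet rule (1) takes the latest of three dates, so a transmission after the last contact sets the date by itself. Rule (2) can be read the same way, crediting 374 days on the strength of a transmission.

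Three groups can transmit beyond their last adverse-event check:

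- **Lost to follow-up, not yet exited.** Protocol 10.23.3 requires "details of a minimum of two attempts and the method of attempt" but sets no deadline. Under 10.23.1, "Subjects will be considered exited upon completion of the study exit e-CRF", so the gap has no stated length.
- **Conditionally disengaged (10.23.6).** Data-collection requirements lapse, though sites are encouraged to collect what they can.
- **Withdrawn without an exit adverse-event review.** Section 10.23.1 lists adverse events among the exit items, but 10.23.4 and 10.23.5 name only the reason for leaving, and only if it can be obtained.

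Unreported events in these tails would raise the Kaplan-Meier estimate and lower the hazard rate, and nothing in the output would show it.

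**Working it through.** **Inputs from the documents.** SAP 6 assumes 60 subjects, 12 months, 2 exacerbations per patient-year, and 50% meeting the event definition. Its figures reproduce: 60 × 2 × 1 = 120 exacerbations; 120 × 0.5 = 60 COPD events. The implied rate is 2 × 0.5 = 1 event per patient-year, so λ = 1/365.25 per day. The horizon is day 374 (SAP 7.9.3). Calls come every 90 days (protocol Table 6 targets).

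**Assumptions, not in the documents.** Constant hazard; loss of 5%, 10% or 20% at a uniformly distributed time; last call before loss = last adverse-event check; transmissions for a further 90 days; a share p of tail events reported anyway.

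**True value.** exp(−374/365.25) = 0.3592, or 35.92% event-free at day 374.

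**Hand check.** Suppose a fraction f had its last check at day 284, transmits to day 374, and p = 0. Then S = (1 − f)·exp(−374λ) + f·exp(−284λ).
- f = 10%: 0.9 × 0.3592 + 0.1 × 0.4595 = 0.369 (+1.0 point).
- f = 20%: 0.8 × 0.3592 + 0.2 × 0.4595 = 0.379 (+2.0 points).

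**Spread-out loss.** The observed hazard is h(t) = λ[R + pG] / [R + pG + (1 − p)G₀]. R is the share event-free and still under ascertainment. G is the share in a tail and truly event-free. G₀ is the share in a tail who were event-free at their last check; under the SAP rule the unreported part stays in the risk set. The estimate is S = exp(−∫h dt), integrated to day 374.

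| Loss | p = 0 | p = 50% | p = 80% | p = 100% |
|---|---|---|---|---|
| 5% | 36.41 (+0.5) | 36.17 (+0.2) | 36.02 (+0.1) | 35.92 (0) |
| 10% | 36.94 (+1.0) | 36.42 (+0.5) | 36.12 (+0.2) | 35.92 (0) |
| 20% | 38.07 (+2.2) | 36.98 (+1.1) | 36.34 (+0.4) | 35.92 (0) |

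Simulation with 2,000,000 subjects agrees to within 0.1 point. At 10% loss the hazard reads 0.973 per year at p = 0 and 0.986 at p = 50%, against 1.00. An extreme case (20% loss, all transmitting to day 374, p = 0) gives 42.8% (+6.9).

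**Precision for comparison.** 1.96 × √(0.359 × 0.641/n) = 0.121 at n = 60 and 0.094 at n = 100, ignoring censoring.

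**Testing remedies (90-day tail; truth 35.92).**

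| Scenario | SAP rule | Date moved, later events kept | One cutoff for both | All gaps reviewed |
|---|---|---|---|---|
| 10% loss, p = 50% | 36.42 | 35.52 | 35.92 | 35.92 |
| 10% loss, p = 80% | 36.12 | 35.28 | 35.92 | 35.92 |
| 20% loss, p = 80% | 36.34 | 34.56 | 35.92 | 35.92 |
| 10% of first events cause loss, 50% reported | 38.04 | 37.60 | 39.38 | 35.92 |
| 10% of first events cause loss, 80% reported | 36.76 | 36.58 | 39.38 | 35.92 |

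Moving the date while keeping later events errs downward when loss is unrelated to exacerbation: at 10% loss and p = 80% it misses by −0.64, against +0.20 for the SAP rule. One common cutoff is right in that setting, but overstates survival (+3.5) when exacerbations cause the loss. The review column assumes the records reveal every unreported event.

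**The case against.** The protocol already limits the problem. Events are reported as they occur, calls and exit collect them, and the inclusion criteria require medical records to be accessible to the site. Under 10.23.1, "Upon exiting from the study, no further study data will be collected", which ends any tail. All of this stands and keeps the group small, but none of it is tied to the censoring date.

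The word usable in SAP 7.9.3 may govern transmissions as well as interrogations, and may mean manual ones that carry the investigational data. That would require an active subject, and 10.11 gives sites a report of missed manual transmissions. The reading is fair and shrinks the group, but does not empty it: a conditionally disengaged subject can still transmit manually.

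An interrogation might seem a safe marker because it usually happens at a visit. That does not hold generally. Section 10.11 accepts an interrogation file in place of missed transmissions with no adverse-event step, and 10.8, 10.12.2 and 10.17 list adverse events only where applicable.

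The strongest objection is proportion: an exploratory curve, no hypothesis, and a bias well inside the confidence interval unless loss is heavy and reporting poor. That is accepted, and it sets the grade.

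**Conclusion.** The rule as written can count unascertained time as event-free, and it should be tightened. Importance is low. With 5% to 20% loss and a 90-day tail, the overstatement of 12-month event-free survival is about 0.5 to 2.2 points with no reporting of tail events and 0.1 to 1.1 points at 50% to 80% reporting. Loss, tail length and reporting are all assumed. With no such subjects, or complete reporting, the bias is zero.

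A reader might infer that the study's main result is compromised, or that the curve is off by many points. The documents support neither. The primary objective rests on plots around adjudicated events, which do not use the censoring date. Large errors need heavy loss, transmission through day 374 and no reporting at all, and nothing in the documents points to that combination. Nor is time between ordinary quarterly calls affected, provided the next call asks about the interval.

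**What to change.** Change SAP 7.9.3 as follows.

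1. Censor event-free subjects at the earlier of day 374 and the last date on which COPD-event status was ascertained: a call or visit that collected adverse events, an exit adverse-event review, or a documented records review. Neither a transmission nor an interrogation without an adverse-event check should set the date, under rule (1) or rule (2).
2. For every subject whose last transmission or interrogation is later than the last adverse-event check, whether or not an event was reported, have the site check the medical records through that date. Do this while consent stands and before the exit form is completed, and use the reviewed-through date.
3. Where no review is obtained, apply the same ascertainment cutoff to events and to censoring. Do not move the censoring date while keeping later-reported events.
4. Report the current transmission-based rule, with all adjudicated events, as one sensitivity analysis, because the common cutoff can err upward if exacerbations themselves cause loss of contact.

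**Cost.** One SAP paragraph, one derived date per subject and one extra run. The records check is a task during conduct, so sites must be told: at most about 3, 6 or 12 of 60 subjects at 5%, 10% or 20% loss. Without review, follow-up time falls by roughly 1%, 2–3% or 5–6%, and a few late events may appear only in the sensitivity analysis. Records that miss some events leave a small residual bias.
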